- 2) Cerebral angiography was performed, and detailed consent was obtained after the study protocol was explained to the participants who met the selection criteria.
- 3) Using a randomization program, the test group (203 patients; aspirin 100 mg + prasugrel 5 mg) and the control group (203 patients; aspirin 100 mg + clopidogrel 75 mg) were classified.
- 4) The above drugs were prescribed according to the assigned group and taken 5 days before the procedure.
- 5) The patients were hospitalized 2 days before the procedure, and whether the drug was taken was checked immediately after hospitalization (if the drug was not taken properly, the patient was excluded from the study).

6) The platelet function test (VerifyNow assay; Accumetrics, San Diego, California, USA) was performed a day before the procedure to check the clopidogrel responsibility and adjust the drug according to the result.

P2Y12 reaction units (PRU) <220

- Clopidogrel group: aspirin 100 mg + clopidogrel 75 mg
- Prasugrel group: aspirin 100 mg + prasugrel 5 mg

PRU ≥220

- Clopidogrel group: aspirin 100 mg + clopidogrel 75 mg + cilostazol 100 mg
- Prasugrel group: aspirin 100 mg + prasugrel 5 mg + prasugrel 5 mg

The morning on the day of the procedure, after administering the drug at the adjusted dose, the planned intracerebrovascular procedure was performed.

7) Brain magnetic resonance imaging (MRI) was performed within 7 days from the day of the procedure (i.e., from the day of the procedure to 1 week after the procedure, and it varied depending on the clinical situation).

8) If there were no neurological abnormalities or complications, the patient was discharged with discharge medication on the next day following the procedure.

- Clopidogrel group: aspirin 100 mg + clopidogrel 75 mg
- Prasugrel group: aspirin 100 mg + prasugrel 5 mg

9) On postoperative day 30 (30-35 days after the procedure), the patient's clinical courses and complications were assessed. If there were no specific findings, the drug was changed to aspirin 100 mg + clopidogrel 75 mg in both groups.

- Time table

Procedure	Screening	Pre-medication	Admission	Medication adjustment	Treatment	Follow-up 1 (MR)	Follow-up 2	Follow-up 3
Time period	Day -60 ~ -6	Day -5 (out-patient)	Day -2 (in-patient)	Day -1 (in-patient)	Day 0 (in-patient)	Day 1 (in-patient)	Day 2 (discharge)	Day 30
Visit window	-	0~± 1 day	0~± 1 day	0 ~+1 day	-	0~+1 day	0~+3 days	0~± 5 days
Informed consent	O	-						
Inclusion/Exclusion Criteria	O	-						

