Demographic data	O	-	O					
Medical History	O	-	O					
Vital sign	O	-	O		O	O	O	O
Neurological examination	O	-	O		O	O	O	O
Aneurysm data	O	-						
Radiologic data	O	-			O	O		
Medication compliance	-	-	O					O
VerifyNow test	-	-	-	O				

Study Population

At the time of initial admission for pretreatment examination, patients were screened based on their medical history, vital sign evaluation, and laboratory tests (hematological tests, biochemical tests, urinalysis, and pregnancy test). Detailed inclusion and exclusion criteria of the present study were as follows:

- **Inclusion Criteria**

- Patients aged between 19 and 75 years
- Aneurysms without any evidence of rupture on an intracranial imaging study within the last 6 months
- Planned treatment with coil embolization with stent insertion or flow diverter insertion
- If the patient itself consented to this study

● **Exclusion Criteria**

- History of acute ischemic stroke or transient ischemic attack
- Any intracranial hemorrhage except subarachnoid hemorrhage due to aneurysm rupture within the last 3 months
- Concurrent treatment other than endovascular procedures (e.g., open craniotomy and microsurgical clipping)
- Contraindications to iodine contrast agents
- Already taking antiplatelet or antithrombotic drugs other than aspirin
- Hypersensitivity to aspirin, prasugrel, or clopidogrel
- Cardiac arrhythmia that should be needed to take anticoagulants
- Pregnant or lactating women
- Chronic kidney disease (GFR <60)
- Patients with chronic liver disease who had at least 100 IU/L of either AST/ALT in the liver function test
- Patients with pathological active bleeding, as seen in peptic ulcer
- Patients with genetic problems such as galactose intolerance, Lapp lactase deficiency, or glucose-galactose malabsorption because they contain lactose
- Patients continuously taking non-steroidal anti-inflammatory drugs and cyclooxygenase-2 inhibitors
- Patients requiring concomitant administration of ≥ 15 mg methotrexate for a week
- If the case was difficult to follow up after treatment

Randomization

Randomization was conducted using the randomization program provided by the Seoul National University Hospital Biomedical Research Institute (<http://mrcc.snu.ac.kr>) and managed by a third party to ensure that the researchers were blinded to the assignments.

Study Endpoints

The primary endpoint was intraprocedural thromboembolic complications or

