postprocedural ischemic stroke or death. The detailed information is as follows:

- A thromboembolism detected during the neurointerventional procedure
- Transient ischemic attack, ischemic stroke, or death with evidence of infarction on diffusion-weighted imaging, occurring within 30 days after the procedure

The secondary endpoints were postprocedural stroke and diffusion-restricted lesions on diffusion-weighted MRI. Another secondary endpoint was the preprocedural platelet function test value and its adjustment ratio. The details are as follows:

- Ischemic stroke in the relevant arterial territory within 30 days after the procedure
- Any stroke, including ischemic and hemorrhagic strokes, within 30 days after the procedure
- Disabling or fatal stroke within 30 days after the procedure
- Diffusion-restricted lesion detected on the 7-day postprocedural MRI

The safety endpoints were bleeding related to P2Y12 antagonists, including any bleeding within 30 days or major bleeding. Bleeding criteria followed the PLATelet inhibition and patient Outcomes bleeding criteria [4,5].

- Major bleeding criteria
 - ✓ Fatal bleeding (bleeding that directly results in death within 7 days)
 - ✓ Intracranial bleeding
 - ✓ Intrapericardial bleeding with cardiac tamponade
 - ✓ Hypovolemic shock or severe hypotension due to bleeding, requiring pressors or surgery
 - ✓ A decline in the hemoglobin level of ≥ 5.0 g/dL
 - ✓ Need for transfusion of at least 4 units of red blood cells
- Other major bleeding criteria
 - ✓ Bleeding that led to clinically significant disability
 - ✓ Decline in hemoglobin level of ≥ 3.0 g/dL but < 5.0 g/dL
 - ✓ Need for transfusion of at least 2-3 units of red blood cells
- Minor bleeding criteria
 - ✓ Any bleeding requiring medical intervention but not meeting the criteria for major bleeding

Determination of the Sample Size

Given the hypothesis of the present study, we used a two-proportion Z-test with pooled variance and set the significance level at 0.05, power = 0.8.

In previous retrospective studies, intraprocedural thromboembolism occurred in the prasugrel group (0.009) and the clopidogrel group (0.064), with a -0.055 difference in the ratio of any stroke and death during the 30-day treatment. A total of 182 samples were required to prove significance at 80% for each group. Considering the 10% dropout rate, 203 patients were required per group, with a total of 406 patients.

Statistical Analysis

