Statistical analysis was performed using SAS®(25) version 9.4 or later versions. All the efficacy analyses were based on the intention-to-treat principle. For comparison of all study endpoints (primary, secondary, and safety), 1) ratio data were analyzed using Pearson's chi-square test and 2) continuous variable comparison was analyzed using an independent two-sample t-test. All statistical tests were based on a two-tailed test with a significance level of 5%, and the safety analysis presented observations without correction for missing values.

- Baseline characteristics

Continuous variables are expressed as the mean \pm standard deviation. Categorical and continuous variables of the baseline characteristics were compared and analyzed using the chi-square or Fisher's exact test and Student's t-test.

- All endpoints

For comparison of all endpoints (primary, secondary, and safety) in the two groups, 1) ratio-type data were analyzed using Pearson's chi-square test and 2) continuous variable comparison was analyzed using an independent two-sample t-test. Statistical significance was set at $P < 0.05$.

- Exploratory subgroup analyses

For the following pre-defined subgroups, subgroup analysis was performed to determine the difference between the overall primary and secondary endpoints.

- ✓ Previous major cardio-cerebrovascular accident
- ✓ Clopidogrel responsiveness (hyporesponder, $PRU \geq 220$; responder, $PRU < 220$)

- ✓ Cerebral aneurysm size in the stent group (<5 mm or \geq 5 mm)
- ✓ Parent artery diameter (mean diameter <2.5 mm or ≥2.5 mm)
- ✓ Procedure (stent-assisted coiling, flow-diverter)
- ✓ Occlusion grade (Roy-Raymond classification)

The difference between the test and control groups according to subgroup followed the regression model with interaction.

Possible Risks and Benefits

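### Step 5 excludes randomised patients who did not take the allocated drug properly, yet all efficacy analyses are called intention-to-treat

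*Combined protocol and SAP*

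**What the plan says.** The numbered steps under Research Design fix the order of events. Step 3 randomises 203 patients to each arm. Step 4 starts the allocated drug: "The above drugs were prescribed according to the assigned group and taken 5 days before the procedure". Step 5 admits the patient two days before the procedure and checks intake at once: "if the drug was not taken properly, the patient was excluded from the study".

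The Statistical Analysis section states without qualification: "All the efficacy analyses were based on the intention-to-treat principle". Its only statement on missing data concerns safety: "the safety analysis presented observations without correction for missing values".

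Other relevant places:

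- Study Population introduces its list with "Detailed inclusion and exclusion criteria of the present study were as follows". Non-adherence is not on that list, and the time table marks the eligibility criteria at screening only.
- The time table has a row for "Medication compliance", marked at admission, so the information is already collected.
- Study Endpoints counts as primary events "A thromboembolism detected during the neurointerventional procedure" and ischaemic events or death within 30 days after the procedure.
- The sample-size section says: "Considering the 10% dropout rate, 203 patients were required per group". It does not say whether step-5 exclusions are part of that 10%.

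**The concern.** ITT keeps randomised patients in their assigned arm whatever their adherence. Step 5 removes patients because of their adherence. Two competent analysts could follow this plan and arrive at different denominators for the primary endpoint, both labelled ITT.

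The removal happens after patients have known exposure to the allocated drug. Intake may depend on tolerability, and adverse events are recorded from consent onwards, so a patient who stopped because of an early adverse event could meet the wording of step 5. Removal can therefore differ by arm, and the groups compared may no longer be the groups randomised. A reader of a result called ITT would not know that anyone had been taken out.

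The gap is wider because the plan gives no criterion for improper intake, does not say whether excluded patients are followed, and has no rule for how a patient without an outcome enters the efficacy analysis.

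**Working it through.** **1. Can the text be reconciled as it stands?** Step 5 is not an eligibility check: it comes after randomisation, and non-adherence is not among the listed criteria. It is not a declared modified ITT, because none is defined. It could mean that the patient leaves study treatment but is still followed and analysed, but no section says so. Read literally, the conflict remains.

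**2. The plan's own sample size.** Inputs from the sample-size section: p1 = 0.009 (prasugrel), p2 = 0.064 (clopidogrel), pooled Z-test, 5%, power 0.80. The Statistical Analysis section makes the test two-sided.

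- p̄ = (0.009 + 0.064)/2 = 0.0365
- √[2p̄(1−p̄)] = 0.2652; √[p1(1−p1) + p2(1−p2)] = 0.2623
- n = (1.960 × 0.2652 + 0.8416 × 0.2623)² / 0.055² = 181.3, rounded up to 182
- 182/0.9 = 202.2, rounded up to 203

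The stated 182 and 203 reproduce. Power = Φ{(|p1−p2|√n − 1.960 × 0.2652)/0.2623} = 80.1% at 182 and 84.3% at 203.

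**3. How many patients.** The documents give no non-adherence rate, so a share f of 2%, 5% or 10% per arm is assumed. Then 203f = 4.1, 10.2 or 20.3 patients per arm.

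**4. When removal biases the comparison.** Let a share f of an arm be removed, and let d be the gap in underlying risk between removed and kept patients. The arm's observed risk shifts by f × d. The contrast is undisturbed only if f × d is equal in the two arms. Unequal f with the same non-zero d, or equal f with unequal d, is each enough to disturb it. The documents give neither f nor d, so the direction and size cannot be computed.

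**5. Dilution if patients are kept.** Give non-adherent patients the same risk r in both arms, since they are assumed to take neither P2Y12 drug. Then

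- prasugrel risk = (1−f) × 0.009 + f × r
- clopidogrel risk = (1−f) × 0.064 + f × r
- difference = (1−f) × (−5.5) = −5.39, −5.23 or −4.95 points for any r

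Two assumed values of r are shown: 6.4%, and double that, 12.8%.

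| Assumed f | 2% | 5% | 10% |
|---|---|---|---|
| Risks at r = 6.4% (prasugrel / clopidogrel, %) | 1.01 / 6.40 | 1.175 / 6.40 | 1.45 / 6.40 |
| Power, all 203 per arm kept, r = 6.4% | 82.2% | 79.0% | 73.0% |
| Risks at r = 12.8% (prasugrel / clopidogrel, %) | 1.138 / 6.528 | 1.495 / 6.72 | 2.09 / 7.04 |
| Power, all 203 per arm kept, r = 12.8% | 81.0% | 75.8% | 66.7% |
| Power under step 5, 199 / 193 / 183 per arm | 83.5% | 82.4% | 80.4% |

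Against step 5, keeping patients costs about 1, 3 or 7 points at r = 6.4%, and about 2.6, 6.7 or 13.6 points at r = 12.8%.

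**6. If the 10% dropout also occurs.** With 182 evaluable per arm and r = 6.4%, keeping patients gives 77.9%, 74.4% or 68.3%. If step-5 exclusions come on top of that dropout (178, 173 or 164 per arm), step 5 gives 79.3%, 78.1% or 75.9%. The allowance itself is 203 − 182 = 21 patients per arm, so 10% non-adherence (about 20) would use nearly all of it.

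**The case against.** The strongest reply is that ITT is named for all efficacy analyses and ordinarily means all randomised patients as assigned, so step 5 may only take a patient off study treatment. That reading is possible, but the plan does not state it, and exclusion from the study is not the usual way to say it.

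Second, step 5 acts shortly before a stent or flow diverter is placed and may be a clinical or stopping rule. This stands. A reader might infer that such patients must continue through the study procedures. The documents do not support that inference, and the point concerns only follow-up and counting.

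Third, exposure before the check is only about three days (Day −5 to Day −2), and exclusion comes before any primary event can occur. This also stands: a reader might infer that patients are removed because of their outcomes, and the order of the steps rules that out for the primary endpoint. It does not rule out removal that differs by arm.

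Fourth, keeping patients costs power, and following them does not by itself yield an outcome: if the procedure is postponed or cancelled, the 30-day window has no starting point. Both are true, and the fix has to deal with them.

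**Conclusion.** The conflict is real and should be resolved before the primary analysis, because it decides who is in that analysis. This conclusion rests on the text: a stated exclusion rule contradicts a stated analysis principle, and no section reconciles them.

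The numerical size is unknown. The 4, 10 or 20 patients per arm and all the power figures rest on assumed non-adherence rates, equal in the two arms, and on assumed risks for non-adherent patients. The 0.11 to 0.55 points between the adherent-only and all-randomised differences are dilution: the two analyses estimate different quantities. They do not measure selection bias.

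Two stronger readings go too far. One is that the result is biased in favour of one drug; the documents give neither removal rates nor risks by arm, so they show that bias is possible, not that it occurred. The other is that the sample size is wrong; 182, 203 and 406 reproduce from the stated inputs.

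**What to change.** Reconcile step 5 with the Statistical Analysis section, leaving the clinical handling of a non-adherent patient as it is:

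1. State that step 5 governs study treatment or procedures only, and does not end follow-up or remove the patient from the analysis.
2. Collect the outcome of every randomised patient where possible. State the time anchor, and a rule for patients whose procedure is postponed or cancelled or whose outcome is missing.
3. Define the primary efficacy analysis as all randomised patients in the assigned arm.
4. Define the adherence criterion, and use the adherent patients only as a per-protocol sensitivity set.
5. Report step-5 exclusions by arm, and say whether the 10% dropout allowance was meant to include them.

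If exclusions have already occurred and outcomes cannot be recovered, report them by arm and do not call the reduced set ITT.

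The cost is a sentence in step 5, short definitions of the two sets, the missing-outcome rule, and follow-up of a few more patients; intake is already recorded at admission. The statistical price is dilution. Under the assumptions shown it is about 1 to 7 points of power relative to step 5 if non-adherent patients have 6.4% risk, and about 2.6 to 13.6 points at 12.8%. With only 182 evaluable per arm, power falls below the planned 80% at every assumed rate.

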Accordingly, the demand for next-generation P2Y12 antagonists has continued, and according to a paper published in 2007, clopidogrel and prasugrel patient responses and platelet activity inhibition were compared before percutaneous coronary intervention [1]. Reportedly, the platelet aggregation inhibitory effect is remarkably high. Choi et al. revealed the efficacy of prasugrel in coil embolization of cerebral aneurysms with stent insertion; the incidence of thromboembolism was significantly lower in the prasugrel group than in the clopidogrel group (0.9% vs. 6.4%; $P = 0.01$), and the bleeding risk was reported to be similar (0.5% vs. 2.2%; $P = 0.22$) [2,3]. However, these recent studies are based on single-center retrospective data; therefore, there is a limit to the level of evidence.

This study aimed to compare the safety and usefulness of prasugrel vs. clopidogrel in patients scheduled to undergo stent or diverter treatment for unruptured cerebral aneurysms.

Specific Aim and Hypothesis

The primary aim of the present study was to investigate the effect of prasugrel in patients undergoing neurointerventional treatment for UIAs (i.e., stent-assisted coiling or flow diverter insertion). The prasugrel and clopidogrel groups were compared to elucidate their safety (hemorrhagic complications) and efficacy (thromboembolic complications) in the periprocedural period. In the present study, we hypothesized that prasugrel has a preventive effect that is not inferior to that of clopidogrel in any treatment group.

Research Design and Methods

Research Design

Patients who visited the outpatient department of neurosurgery at multiple institutions (Severance Hospital, Gangnam Severance Hospital, Yongin Severance Hospital, Ewha Womans University Seoul Hospital, Bucheon St. Mary's Hospital, and International St. Mary's Hospital) were screened to participate in the present research. After following the study protocol, the participants were divided into the prasugrel and clopidogrel groups by 1:1 randomization.

- Detailed information of the study protocol
- 1) After patients with UIAs were hospitalized, baseline characteristics were obtained, and blood tests, including renal function test (glomerular filtration rate [GFR]), liver function test (aspartate aminotransferase [AST]/alanine aminotransferase [ALT]), and pregnancy test, were performed.

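### The time table allows the final visit on Day 25–29, before the 30-day endpoints close, although step 9 places it at Day 30–35

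*Combined protocol and SAP*

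**What the plan says.** **Timing of the final assessment.** In the Combined protocol and SAP, step 9 of the detailed study protocol reads "On postoperative day 30 (30-35 days after the procedure" and assigns the review of clinical course and complications to that visit. The time table lists the same visit as Follow-up 3, Day 30, with a visit window written as zero, a tilde and ± 5 days.

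**What happens at that visit.** In the time table, the row "Neurological examination" is marked through Follow-up 3, which is the last column. No later visit or telephone contact is described. Step 9 also says: "If there were no specific findings, the drug was changed to aspirin 100 mg + clopidogrel 75 mg in both groups".

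**Endpoints that depend on it (Study Endpoints).**
- Postprocedural primary component: "occurring within 30 days after the procedure".
- Stroke secondary endpoints: three, all with a 30-day limit, for example "Any stroke, including ischemic and hemorrhagic strokes, within 30 days after the procedure".
- Safety: "any bleeding within 30 days or major bleeding".

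**Analysis.** The Statistical Analysis section states intention-to-treat for efficacy, compares proportions by Pearson's chi-square test, and leaves missing safety values uncorrected. It does not say how a patient last assessed before Day 30 is counted.

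**The concern.** A site that schedules from the table can close a patient's scheduled follow-up while the 30-day endpoints are still open. A site that schedules from step 9 cannot. Six institutions are named in the Research Design section, so the two texts could be applied differently.

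The endpoints are analysed as simple proportions, which assumes that each patient was observed for the same period. A patient seen without an event on Day 26 would ordinarily enter as event-free to Day 30, although nobody was scheduled to look at Days 27 to 30. At stake is whether the 30-day limit means the same thing for every patient. This is a conflict between two stated rules, one of which also conflicts with the endpoint definition. It is not a matter of missing detail.

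**Working it through.** **Inputs.** Step 9: Day 30 to Day 35. Time table: Day 30 with a ± 5 day window, and the procedure on Day 0. Study Endpoints: observation through Day 30.

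**1. Is the table window two-sided?** The notation is loose, so the rest of the row matters. Follow-up 1 and Follow-up 2 have plus-only windows (+1 day and +3 days), as does the medication-adjustment visit (+1 day). Pre-medication and admission have ± 1 day. The table thus distinguishes plus-only from two-sided windows, and the ± at Follow-up 3 is fairly read as two-sided. If it is a slip for a plus sign, the cell still needs correcting.

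**2. The two windows.**
- Table: 30 − 5 = Day 25 to 30 + 5 = Day 35.
- Step 9: Day 30 to Day 35.
- Days 30 to 35 satisfy both texts. Days 25 to 29 satisfy only the table.

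**3. Endpoint days left uncovered.** For a last visit on Day d, the uncovered days are 30 − d, and their share of the period is (30 − d)/30.

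| Last visit | Uncovered days | Share of the 30 days |
|---|---|---|
| Day 25 | 5 | 16.7% |
| Day 26 | 4 | 13.3% |
| Day 27 | 3 | 10.0% |
| Day 28 | 2 | 6.7% |
| Day 29 | 1 | 3.3% |
| Day 30 or later | 0 | 0% |

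These are shares of days, not of events.

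**4. Which endpoints are touched.** The postprocedural primary component, the three 30-day stroke endpoints and any bleeding within 30 days are touched. Thromboembolism detected during the procedure is not, because it is recorded on Day 0.

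**5. Does anything else close the gap?** The adverse event section evaluates events from consent and sets no end date for new ones, so an event after an early visit can still be reported. It schedules no contact to look for such events. Its explicit provision after the last visit concerns events already ongoing.

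**6. Does the table move the drug change?** The change is written only in step 9, which carries its own Day 30 to 35 window and makes the change conditional on there being no specific findings. The time table has no row for it.

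**The case against.** The strongest reply is that little would be lost. Late endpoint events are mostly ones that bring a patient to care: stroke, transient ischemic attack, death, or bleeding whose mildest listed class needs medical intervention. The adverse event section lists death and hospital admission among serious events and requires a report to the review board within 24 hours of recognition. Patients who would be difficult to follow up are excluded. The stated aim is a comparison "in the periprocedural period", so few events may fall near Day 30. All of this stands and keeps the point minor. It does not remove it, because reporting within 24 hours begins only once someone has recognised the event, and no contact at Day 30 is planned for a patient seen earlier.

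Two stronger readings are tempting, and the documents support neither.

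- **A reader might infer that up to 17% of events could be missed, with a matching loss of power.** That treats a share of days as a share of events. The documents give no event timing. The sizing text says "intraprocedural thromboembolism occurred in the prasugrel group (0.009) and the clopidogrel group (0.064", and events of that kind cannot be missed through an early final visit. The same sentence goes on to mention stroke and death over 30 days, so the label is itself unclear. It is no basis for projecting late event counts in either direction.
- **A reader might infer that an early visit ends the randomised comparison before Day 30.** That would require a site to take the drug change from step 9, ignore the window in that same step, and borrow the table's window instead. This is a possible misreading, not something the plan schedules.

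**Conclusion.** The point holds as a minor internal contradiction. The table permits a final visit on Days 25 to 29, step 9 does not, and a visit on those days leaves 1 to 5 of the 30 endpoint days without scheduled ascertainment. The conclusion rests on the two-sided reading of the table's window, which the rest of the row supports, and on the absence of any later scheduled contact.

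The effect on results cannot be estimated from the documents and may be close to nil. They give neither the timing of events nor the number of patients seen early. No change in the primary test or in a bleeding test is claimed, and no difference between arms is shown. The case for acting is that every patient should have the same observation period and that securing it is cheap.

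**What to change.** - Reconcile the Follow-up 3 window in the time table with step 9.
- State that primary, stroke and bleeding status through Day 30 is established at or after Day 30 for every patient. For anyone seen earlier, confirm status once Day 30 has passed.
- If visits are already complete, as the past tense of much of the text suggests they may be, report by arm how many patients were last assessed before Day 30.
- The investigators should confirm that the table's window does not move the drug change described in step 9. No timing for that change is proposed here.

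**Cost.** One table cell and one sentence, or one count by arm if visits are complete. The downside is slightly less flexible scheduling of the final visit, or a brief status check for patients seen early.

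### The safety endpoint restricts bleeding to drug-related events with no rule for judging relatedness, and does not say which grades make up any and major bleeding

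*Combined protocol and SAP*

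**What the plan says.** Study Endpoints defines the safety outcome in one sentence: "The safety endpoints were bleeding related to P2Y12 antagonists, including any bleeding within 30 days or major bleeding". It then adopts one named grading scale and prints three grades: major, "Other major bleeding criteria", and minor. The minor grade, the lowest listed, is "Any bleeding requiring medical intervention but not meeting the criteria for major bleeding". None of the printed criteria asks whether the bleed was caused by the study drug.

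Four other places bear on how the sentence will be applied:

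- **Specific Aim and Hypothesis** sets out to compare the groups on "their safety (hemorrhagic complications) and efficacy (thromboembolic complications) in the periprocedural period", so bleeding is the safety half of the aim.
- **Randomization** says the allocation was "managed by a third party to ensure that the researchers were blinded to the assignments".
- **Research Design**, steps 4 and 6, has the drugs prescribed by assigned group and, at PRU of 220 or more, adjusted differently by arm: "Clopidogrel group: aspirin 100 mg + clopidogrel 75 mg + cilostazol 100 mg" against "Prasugrel group: aspirin 100 mg + prasugrel 5 mg + prasugrel 5 mg". No placebo or double-dummy is described.
- **Statistical Analysis** compares safety proportions by Pearson's chi-square test at a two-sided 5% level.

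**The concern.** The causal condition and the words about any bleeding cannot both decide which events are counted. If the condition is applied, an access-site haematoma or an intracranial bleed during the procedure can be put down to the procedure and dropped. In this trial every patient has an invasive procedure while taking aspirin plus a P2Y12 inhibitor, so many bleeds could reasonably be attributed to either cause. The plan names no assessor, criteria or adjudication for that judgement. If whoever decides knows or can guess the arm, attribution may differ between arms, and the comparison would then reflect opinion as well as bleeding.

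Two further gaps affect the count even if causality is ignored:

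- **Floor.** A bleed needing no intervention is a bleed, but it meets no listed grade.
- **Grouping.** The text does not say whether the other-major grade belongs to major bleeding.

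The safety sentence also gives a 30-day period without saying when it starts.

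**Working it through.** **1. The plan's own figure.** The sample size concerns thromboembolism, not bleeding. With 0.009 versus 0.064, pooled variance, two-sided 5% and 80% power, the mean proportion is 0.0365:

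n = [1.960·√(2·0.0365·0.9635) + 0.8416·√(0.009·0.991 + 0.064·0.936)]² / 0.055² = (0.5198 + 0.2208)² / 0.003025 = 181.3, so 182 per group.

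Then 182/0.9 = 202.2, so 203. The stated figures reproduce. They neither support nor weaken this point, since no power or margin is stated for bleeding.

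**2. Expected bleeds.** The only bleeding rates in the document are those of the retrospective comparison cited under Possible Risks and Benefits: 0.5% on prasugrel and 2.2% on clopidogrel.

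- At 203 per arm: 203·0.005 = 1.0 and 203·0.022 = 4.5.
- At 182 per arm: 0.9 and 4.0.

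**3. What one reclassified bleed does.** With equal arms of n, events a and b, and t = a + b, Pearson's statistic reduces to 2n(a − b)² / [t(2n − t)]. The 5% cut-off is 3.84. At n = 203:

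| Events | Statistic | P |
|---|---|---|
| 1 vs 4 | 406·9/(5·401) = 1.82 | 0.18 |
| 0 vs 4 | 406·16/(4·402) = 4.04 | 0.044 |

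Calling the single prasugrel bleed procedure-related would move the result from clearly non-significant to nominally significant.

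**4. Differential attribution (hypothetical).** Suppose the true bleeding rate is equal in both arms and only bleeds called drug-related are counted. The counted rate in each arm is the true rate times the share so called. The rejection probability comes from exact enumeration of two binomials with 203 per arm, using Pearson's test without correction at two-sided 5%. The true rates and attribution shares are assumptions; only the 2.2% is a figure from the plan.

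| True rate, both arms | Called drug-related (prasugrel / clopidogrel) | Counted rates | Expected counted events | Chance of P<0.05 |
|---|---|---|---|---|
| 2.2% | 80% / 40% | 1.76% / 0.88% | 3.6 / 1.8 | 11% |
| 2.2% | 70% / 50% | 1.54% / 1.10% | 3.1 / 2.2 | 6% |
| 6% | 80% / 40% | 4.8% / 2.4% | 9.7 / 4.9 | 25% |
| 6% | 70% / 50% | 4.2% / 3.0% | 8.5 / 6.1 | 10% |
| 6% | no filter | 6% / 6% | 12.2 / 12.2 | 4.7% |

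The inflation depends on both the true rate and the size of the imbalance, and is small when both are small.

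**5. The passages side by side.** The lead sentence restricts by cause, and the printed criteria do not. The section on adverse events states explicitly that events count whether or not a drug caused them; the bleeding endpoint has no matching statement. The plan therefore does not settle whether the causal phrase is a filter or a label.

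**The case against.** The best defence is that the causal phrase is only a label explaining why bleeding is the safety outcome. On that reading the plan has two nested endpoints, any and major, graded on one named scale, and any bleeding means any bleed meeting a listed grade. This is natural and may well be what was meant. But the plan does not say so, and the literal wording supports the opposite.

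Several points on this side stand:

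- A reader might infer three rival definitions. The text supports less: one conflict over attribution, plus an unclear floor and grouping. The phrase in the aim is a summary, not another definition.
- A reader might infer that relatedness is judged unblinded. The document does not say that. It says the researchers were blinded to assignments. The arm-specific drugs and adjustments make effective blinding doubtful, but that is an inference. What can be said is that the two passages are not reconciled and that no assessor is named.
- A reader might suppose that the wording destroys otherwise adequate power to detect excess bleeding on prasugrel. That needs an assumed excess, whereas the document's only rates run the other way. At those rates power at 203 per arm is only about 30% by exact enumeration, so low power does not come from the wording.
- Nothing in the document shows that untreated bleeds would outnumber the clinically relevant ones.
- Adverse events are recorded whatever their cause, and haemorrhagic stroke is counted separately within any stroke without a causal condition. A cause-free bleeding count should therefore be recoverable.

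**Conclusion.** The point holds as a defect in the safety endpoint's definition. The sentence states a restriction which, if followed, allows procedure-attributed bleeds to be dropped from a formal two-sided 5% comparison, with no criteria or assessor for the decision. Which bleeds form the any and major categories is also not fully stated.

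With about 1 versus 4 events expected from the plan's own rates, one reclassified bleed can cross the 5% line. The probability of a false difference is roughly 6% to 25% over the assumed scenarios, against a nominal 5%; the upper end needs both a 6% true rate and an 80%/40% split. These figures show sensitivity. They do not forecast what happened, and the document does not establish that attribution differed by arm. The primary endpoint and the sample size are unaffected. The matter should be corrected, but it does not undermine the trial as a whole.

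**What to change.** Replace the safety sentence in Study Endpoints with:

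> *The safety endpoints are (a) any bleeding meeting the major, other major or minor criteria below, and (b) major bleeding (major or other major), within 30 days after the procedure, regardless of relationship to study drug or procedure.*

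State that the window includes the procedure itself, so that intraprocedural bleeds count. Report investigator-judged relatedness, and any recorded bleeding that needed no intervention, descriptively only. Bleeds between the first dose and the procedure fall outside this window and can be listed from the adverse-event records. State who grades the bleeds and whether that person knows the arm, and reconcile the blinding statement under Randomization with the arm-specific drugs under Research Design.

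The cost is a wording change in the protocol and analysis plan, with no extra data. The downside is modest: bleeds caused by the procedure and unrelated to the drug enter both arms and add some noise.
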